8.4. Handling of Missing Data

Algorithms for imputing partial or missing dates are shown below in Table 2. Adverse event end dates are imputed to facilitate calculation of AE duration. Missing or partial death dates will be imputed based on last contact date.

Table 2: Partial or Missing Date Imputation Rules

Variable	Missing Day	Missing Day, Month	Missing Day, Month,
			Year

CONFIDENTIAL Page 21 of 29

Date of Prior Therapy/Date of Initial Diagnosis Adverse Event Start Date	Assign 1 Assign first day of month unless it is the month of first dose of study drug. Otherwise, assign date of first dose of study drug or AE end date (if not missing)	Assign January 1 if prior to date of informed consent, otherwise use date of informed consent. Assign January 1 unless the year is year of first dose of study drug. Otherwise, assign date of first dose of study drug or AE end date (if not missing)	Missing (do not impute) Assign date first dose of study drug.
Adverse Event/Medication End Date	whichever is earlier. Assign the last day of the month or death date or data cut-off date (or end of study date), whichever is earliest.	whichever is earlier. Assign December 31 or death date or data cut-off date (or end of study date), whichever is earliest.	If ongoing, end date is missing. Otherwise, assign death date or data cutoff date (or end of study date), whichever is the earliest.
Medications Start Date	Assign 1 unless it is the month of first dose of study medication. Otherwise, assign date of first dose of study drug or imputed medication end date whichever is earlier.	Assign January 1 unless the year is year of first dose of study medication Otherwise, assign date of first dose of study drug or imputed medication end date whichever is earlier.	Assign date first dose of study.
Death date	Assign 1 unless before the last contact date. Otherwise, assign the day after the date of last contact.	Assign January 1 unless before the last contact date. Otherwise, assign the day after the date of last contact.	Assign the day after the date of last contact.

8.5. Multiple Comparisons/Multiplicity

To control familywise type-I error at 0.05 level, the hypothesis tests for treatment difference will be performed according to the hierarchical testing sequence below:

- 1. PFS by IRR in Ex11 ITT (two-sided 0.05 level)
- 2. PFS by IRR in AP ITT (two-sided 0.05 level)
- 3. ORR by IRR in Ex11 ITT (two-sided 0.05 level)
- 4. ORR by IRR in AP ITT (two-sided 0.05 level)
- 5. OS in Ex11 ITT (two-sided 0.05 level)

CONFIDENTIAL Page 22 of 29

6. OS in AP ITT (two-sided 0.05 level)

The testing starts from PFS in Ex11 ITT and each subsequent endpoint will only be tested if all the testing preceding to it have been statistically significant. If the testing for any endpoint fails to meet statistical significance, the testing and p-value for all the subsequent endpoints will be nominal and statistical significance won't be claimed for all the subsequent endpoints.

8.6. Examination of Subgroups

Subgroup analysis will be performed for the primary and key secondary efficacy endpoints in subgroups of patients defined by the following variables:

- Age (<65 vs ≥65)
 <65 years
 ≥65 years
 65 74 years
- Gender (Male vs. female)
- Race (White vs non-White vs Not-reported)
- Region (North America, South America, Europe, Asia-Pacific)
- Screening ECOG (0 vs. 1 vs. 2)

 \circ \geq 75 years

- Mutation type [KIT exon 9 vs. KIT exon 11 vs. KIT/PDGFRA WT vs. other KIT {absence of exon 9 or 11}/PDGFRA]
- Intolerance to Imatinib treatment (yes vs. no)
- Sum of longest diameters of target lesions at baseline (by tertiles)
- Time Since Initial Diagnosis (by tertiles)
- Best Overall Response to The Most Recent Imatinib Treatment (CR/PR, SD, PD, NE, Missing)

The efficacy endpoints in the patient subgroups will be tabulated by treatment arm and displayed in forest plots.

Subgroup analysis will be performed in the Ex11 ITT Population and AP ITT Population.

8.7. Interim Analysis

No interim analyses are planned for the primary endpoint of PFS based on IRR, or the key secondary endpoint of ORR. The interim analyses of OS will be performed as described in Section 2.3.

8.8. Data Monitoring

The Independent Data Monitoring Committee (IDMC) will consist of an experienced biostatistician and two qualified clinicians, who are not employees of the Sponsor, with

CONFIDENTIAL Page 23 of 29

combined scientific expertise in general oncology and GIST and practical experience conducting clinical studies and monitoring safety and efficacy of clinical studies. The IDMC or Sponsor may request an ad hoc meeting for any reason, including significant unexpected safety event, follow-up of an observation during a planned IDMC meeting, or a report external to the study, such as publication of study results from a competing product. The IDMC objectives and operational details will be defined in the IDMC Charter.

9. SAFETY ANALYSIS

Exposure to study treatment and all safety assessments data will be analyzed in Safety Population and Ex11 Safety Population.

9.1. Study Drug Exposure

Treatment duration, total dose, and relative dose intensity will be summarized as continuous variables using descriptive statistics and categorized as appropriate. For each treatment arm, person year will be calculated. In addition, the number and percent of patients with at least one dose increase and reduction, will be summarized.

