2.1.3. Other Secondary Objectives

- To assess the quality-of-life (QOL) during treatment as measured by:
 - EORTC QLQ-C30
 - Dermatology Life Quality Index (DLQI)
 - GP5 question from the FACT-G (burden of side-effects)
 - EuroQol Visual Analogue Scale (EQ-VAS)
- To assess Time to Tumor Progression (TTP) by independent radiologic review
- To assess efficacy parameters including, disease control rate (DCR), PFS based on Investigator assessment, duration of response (DOR) and time to response (TTR)
- To assess efficacy based on Choi criteria by independent radiologic review

CONFIDENTIAL Page 7 of 29

- To assess the PK/PD relationship of ripretinib
- To compare the safety profile of ripretinib to the safety profile of sunitinib

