2.3. Determination of Sample Size

The sample size selection of 426 patients (n=213 ripretinib, n=213 sunitinib) was based on considerations for powering of the primary endpoint, secondary endpoints, detection of rare safety events and overall exposure to ripretinib. Patients will be randomized in a 1:1 ratio of ripretinib versus sunitinib.

Under the assumptions that median progression-free survival (mPFS) is 9 months for ripretinib and 6 months for sunitinib, the HR is about 0.667 for All Patients (AP) PFS (ripretinib vs sunitinib). A total of 262 events will be required to achieve a statistical power of 90% to test the hypothesis of no difference between ripretinib and sunitinib in AP. Accrual of 426 patients (213 in ripretinib and 213 in sunitinib) within 21 months is expected to have 262 PFS events occurred after additional 8 months of follow up. This has accounted for 20% of dropout rate (discontinuation without progressive disease per IRR or death).

It is further assumed that the mPFS is 9 months for patients with a KIT Exon 11 primary mutation (Ex11) in ripretinib and 5 months for KIT Ex11 in sunitinib, the HR is 0.556 for the KIT Ex011 PFS. A minimum of 151 PFS events in KIT Ex11 population have at least 95% power to test the hypothesis of no difference between ripretinib and sunitinib in KIT Ex11 population.

No interim analysis is planned for PFS based on IRR. The final analysis of PFS based on IRR will be performed in the Ex11 ITT population and in the AP ITT population (as defined in Section 4) using the same data cutoff, following the hierarchical testing sequence specified in Section 8.5. This final analysis is planned to occur when at least 151 PFS events in Ex11 ITT population and approximately 262 PFS events in AP ITT population have occurred. The analysis of PFS in Ex11 ITT population and AP ITT population will be based on the actual number of events observed in Ex11 ITT population and AP ITT population, respectively, at the time of final analysis of PFS.

CONFIDENTIAL Page 9 of 29

At the time of final analysis of PFS by IRR, ORR by IRR and OS in Ex11 ITT and AP ITT will be tested hierarchically as specified in Section 8.5. If all the testing preceding OS are statistically significant, OS in Ex11 ITT will be tested at 2-sided 0.05 significance level; if OS in Ex11 ITT is statistically significant, OS in AP ITT will be tested at 2-sided 0.05 significance level.

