The p-value from a 2-sided stratified log-rank test at 0.05 significance level will be used for evaluation of treatment difference. Point estimate of hazard ratio will be obtained from a Cox proportional-hazards regression model stratified by randomization stratification factors per IRT and the associated 95% CI will be obtained using Wald method. PFS time will be summarized via Kaplan-Meier (KM) methodology using the percentiles (25th, 50th [median], and 75th), survival probabilities at pre-specified timepoints with associated 2-sided 95% confidence intervals, and KM plot of the estimated survival functions.

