9.1.2. Study Drug Exposure in Sunitinib Arm

For sunitinib arm, treatment duration will be calculated as (last dose date - first dose date + 1 day)/30.4375 months.

The cumulative dose (mg) of sunitinib in a cycle is the sum of the actual dose levels that the patient received within the cycle (ie, total dose administered). Total cumulative dose of sunitinib will be calculated as the total amount of doses received on study.

RDI in a cycle will be calculated as (cumulative dose received in the cycle)/(50*7*4 mg)×100%.

Overall RDI will be calculated as (total cumulative dose received)/(Total number of cycles started*[50*7*4])×100%.

CONFIDENTIAL Page 24 of 29

Person year will be calculated as the sum of (last dose date before discontinuation treatment – first dose date + 1 day)/365.25.

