9.2. Adverse Events

Adverse events tables will summarize the number and proportion of patients with an event by SOC and PT for the Safety Population and Ex11 Safety Population. All tables will only include treatment emergent AEs (TEAEs), where TEAEs are defined as any AE which occurs after the administration of the first dose of study drug and through 30 days after the last dose of study drug or the day before the start of subsequent new anticancer drug therapy, whichever occurs first. Drug-related AEs reported after 30 days after the last dose of study drug will also be considered TEAEs. Listings will include all reported AEs, flagging events that were TEAEs. In the case of missing start and/or stop date, non-missing date parts will be used to determine if an AE is treatment-emergent or not. An AE will be categorized as TEAE if a determination cannot be made using the non-missing date parts as to when the event occurred relative to study drug administration. Adverse event toxicity grade will be classified using NCI-CTCAE Version 5.0 criteria. For incidence summaries, a missing toxicity grade of a TEAE will be conservatively imputed as severe; for a TEAE missing causal relationship to study treatment, a causality of "related" will be assigned. Listings will include all reported AEs, flagging events that were TEAEs and displaying missing start/stop dates, severity grades and causalities as they were entered in the clinical database.

An overall summary of the number of patients with TEAEs will be presented, including the number and percentage of patients with any TEAEs, serious TEAEs (TESAE), drug-related TEAEs and TEAEs leading to dose modification, treatment discontinuation, and death.

The number and percentage of patients reporting TEAEs in each treatment arm will be tabulated by SOC and PT; by PT; by SOC, PT, and maximum severity. If a patient has multiple occurrences of the same SOC and PT, then the patient will be counted only once for the SOC and PT using the most severe occurrence for the summarization by maximum severity. Presentation by SOC and PT will display SOC sorted alphabetically and PT by descending frequency based on frequencies observed in the ripretinib arm.

TEAEs and drug-related TEAEs will be summarized by SOC and PT, PT in descending frequency. TEAEs and drug-related TEAEs leading to dose modification, study treatment discontinuation, and TESAEs leading to death will be summarized by SOC, PT, and treatment arm.

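### Adverse events are to be compared only as crude patient proportions, although treatment runs to progression and the design assumes longer PFS on ripretinib; the person-years calculated are used in no AE analysis

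*SAP*

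**What the plan says.** SAP 2.1.3 lists among the other secondary objectives: "To compare the safety profile of ripretinib to the safety profile of sunitinib". Protocol 2.2.2 has the same objective.

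SAP 9.2 sets the measure: "Adverse events tables will summarize the number and proportion of patients with an event by SOC and PT". The list that closes the section (any AE, by grade, drug-related, serious, AESI, fatal and so on) is also in numbers and percentages of patients. It contains no rate per person-year, time-to-first-event or cumulative-incidence analysis. Protocol 9.8.6.1 adds a count of events and rules out formal testing of AE incidence; the SAP adds no test.

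SAP 9.1 states "For each treatment arm, person year will be calculated". The formulas in 9.1.1 and 9.1.2 have the same form; the sunitinib one begins "Person year will be calculated as the sum of (last dose date before discontinuation treatment" and subtracts the first dose date. Neither is referred to again.

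The TEAE window in SAP 9.2 is the same for both arms. It opens at first dose and closes 30 days after last dose, or the day before new anticancer drug therapy if that is earlier. Drug-related events reported later still count as TEAEs.

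SAP 2.2.2 ties treatment to progression on independent review, unacceptable toxicity or withdrawal of consent.

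**The concern.** A crude percentage counts patients with at least one event during however long they were observed. If one arm is observed longer, its percentage is higher even when the monthly risk is the same. Here observation time depends on the efficacy outcome, so the distortion would run against whichever drug delays progression longer. SAP 9 also repeats the safety analyses in the Ex11 Safety Population, where the assumed PFS gap is widest.

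At stake is how a reader weighs the two columns of the AE tables. No primary or key secondary test is affected.

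**Working it through.** **1. The plan's own figures.** The assumed all-patient median PFS "is 9 months for ripretinib and 6 months for sunitinib, the HR is about 0.667". SAP 2.3 continues: "A total of 262 events will be required to achieve a statistical power of 90"%. SAP 8.1 gives the test: "The p-value from a 2-sided stratified log-rank test at 0.05 significance level". With HR 0.667, two-sided 0.05, 90% power and 1:1 allocation:
- Schoenfeld: 4 × (1.960 + 1.282)² / (ln 0.667)² = 257 events.
- Freedman: (1.960 + 1.282)² × (1.667/0.333)² = 264 events.
- Power at 262 events: 90.6%.

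For Ex11 the plan assumes 9 months on ripretinib and "5 months for KIT Ex11 in sunitinib, the HR is 0.556"; 151 events give 95.0% power. Both stated figures reproduce.

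**2. From PFS to time on treatment.** The documents give no treatment duration, so these are assumptions:
- Treatment ends at a PFS event, dropout or data cutoff, each arm exponential, with exit hazard h = ln 2/median + g, where g is the dropout hazard.
- Accrual is uniform over 21 months with 8 more months of follow-up (SAP 2.3), so potential follow-up runs from 8 to 29 months.
- The time base of the 20% dropout is not stated. I took g = 0, g = 0.0186 per month (20% per year), and g = 0.0284 per month (20% of all patients dropped out by cutoff).

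Mean time on treatment: M(h) = (1/h) × [1 − (e^(−8h) − e^(−29h)) / (21h)].

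Example with g = 0. Sunitinib: h = 0.1155, M = (1/0.1155) × [1 − (0.397 − 0.035)/2.426] = 7.4 months. Ripretinib: h = 0.0770, M = (1/0.0770) × [1 − (0.540 − 0.107)/1.617] = 9.5 months. Ratio 1.29.

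**3. From exposure to crude incidence.** With one constant AE hazard λ in both arms, the proportion with an event on treatment is λ × M(λ + h). I set λ so that sunitinib shows 20%, then read off ripretinib. With g = 0, λ = 0.0327 per month and ripretinib shows 0.0327 × 7.63 = 25.0%. The second figure in each incidence column extends the window 30 days past last dose.

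| Dropout | Mean months, sunitinib / ripretinib | Ratio | Ripretinib % when sunitinib is 20% | Ex11 ratio | Ex11 ripretinib % |
|---|---|---|---|---|---|
| None | 7.4 / 9.5 | 1.29 | 25.0; 24.4 | 1.48 | 27.9; 26.9 |
| 20% per year | 6.6 / 8.4 | 1.27 | 24.5; 23.9 | 1.43 | 27.1; 26.1 |
| 20% by cutoff | 6.3 / 7.8 | 1.25 | 24.3; 23.7 | 1.41 | 26.7; 25.8 |

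At fixed hazards of 0.02, 0.05 and 0.10 per month, the all-patient gap on treatment is about 3, 5-6 and 7-8 percentage points. On a matching at-risk denominator the rate ratio would be 1.0 in every row.

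**4. Would the SAP 9.1 person-years do as the denominator?** They stop at last dose; TEAEs continue for up to 30 days (0.99 month). That tail is 10-13% of mean ripretinib time (0.99/9.5 to 0.99/7.8) and 13-16% of mean sunitinib time (0.99/7.4 to 0.99/6.3). Both rates would be too high, and their ratio would be off by about 3%: 1.104/1.134 = 0.973 with no dropout.

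**5. The sunitinib off-weeks.** For n completed cycles the formula counts 42(n − 1) + 28 days, so breaks between cycles are included and only the final 14 days can be lost. That is 33% of time at one cycle, 11% at three and 5.6% at six. If every patient lost all 14 days, the loss would be 213 × 14/365.25 = 8.2 person-years out of about 111-131, or 6.2-7.4%.

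**The case against.** The best defence is that crude incidence answers a legitimate question: how many patients had the event on treatment as given. The comparison is descriptive and no decision rule depends on it. Treatment duration, dose intensity and person-years are reported by arm, so a reader can see any exposure difference. An exposure-adjusted rate brings its own constant-hazard assumption. All of this stands, and it is why the point is an addition to the crude tables rather than a correction of an error. It does not remove the gap: a reader given the percentages and mean exposure separately cannot derive the adjusted comparison for each event, because time at risk to first event is not shown.

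A reader might also infer that the person-year formula undercounts sunitinib in particular, because a patient who stops after the two-week break loses those days. The documents do not support this as an arm-specific defect. The formula is the same in both arms, off-weeks between cycles are counted, and the final 14 days fall inside a 30-day tail that both arms lose.

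**Conclusion.** The point holds as a modest gap in the safety analysis. If PFS differs as assumed and AE hazards are equal and constant, crude tables would show about 24-25% on ripretinib against 20% on sunitinib, and about 26-28% in Ex11. The size rests on exponential time on treatment, treatment ending with PFS, the planned accrual and follow-up, and the dropout readings shown. Stopping for toxicity and the extendable two-year treatment limit were not modelled. Events that cluster early would be distorted less, and if PFS does not differ this source of imbalance disappears.

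Two stronger readings are not supported:
- **Planned exposure of 9 vs 6 months.** Those are assumed PFS medians. Cutoff and dropout bring the mean exposure ratio down from 1.5 to 1.25-1.29.
- **Skin AESIs hit hardest because they accrue with time.** Protocol 1.3.2.1.2 says only that their relation to the drug is unclear; it gives no time pattern.

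**What to change.** In SAP 9.2, for both the Safety and Ex11 Safety Populations, add exposure-adjusted incidence beside the crude tables: patients with a first event divided by person-years at risk. Do this for TEAEs, Grade 3 or higher, SAEs and AESIs.

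- **Time at risk.** From first dose to the earliest of first event, last dose plus 30 days, the day before new anticancer drug therapy, death or data cutoff. Apply the same rule in both arms. This needs a common fallback for an unknown last dose date, which SAP 9.1.1 gives for ripretinib but 9.1.2 does not give for sunitinib.
- **Late drug-related events.** SAP 9.2 counts them as TEAEs beyond day 30. Leave them out of the rate numerator and keep them in the crude tables, so that numerator and denominator cover the same window.
- **Denominator.** Do not reuse the SAP 9.1 person-years unmodified. Keep them as an exposure summary.

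The cost is a few table columns from data already collected, plus a note that the rate assumes a roughly constant hazard. No endpoint, alpha or trial conduct changes. Fixing the definition before results are seen also avoids an adjustment that might later look chosen to favour the sponsor's drug.

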9.1.1. Study Drug Exposure in Ripretinib Arm

For ripretinib arm, treatment duration will be calculated as [(last dose date – first dose date) + 1 day]/30.4375 months. If last dose date is unknown, the earliest of the end of treatment date, data cut-off date (or end of study date), and death date will be used.

The cumulative dose (mg) of ripretinib in a cycle is the sum of the actual dose levels that the patient received within the cycle (ie, total dose administered). Total cumulative dose will be calculated as the total amount of doses received on study.

Relative dose intensity (RDI) for a cycle will be calculated as (cumulative dose in the cycle)/(number of days in the cycle×150mg) ×100%.

Overall RDI will be calculated as (total cumulative dose)/(treatment duration [days]×150 mg) ×100%.

Person year will be calculated as the sum of (last dose date before discontinuation treatment – first dose date + 1 day)/365.25 of all patients.

9.1.2. Study Drug Exposure in Sunitinib Arm

For sunitinib arm, treatment duration will be calculated as (last dose date - first dose date + 1 day)/30.4375 months.

The cumulative dose (mg) of sunitinib in a cycle is the sum of the actual dose levels that the patient received within the cycle (ie, total dose administered). Total cumulative dose of sunitinib will be calculated as the total amount of doses received on study.

RDI in a cycle will be calculated as (cumulative dose received in the cycle)/(50*7*4 mg)×100%.

Overall RDI will be calculated as (total cumulative dose received)/(Total number of cycles started*[50*7*4])×100%.

CONFIDENTIAL Page 24 of 29

Person year will be calculated as the sum of (last dose date before discontinuation treatment – first dose date + 1 day)/365.25.

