Dose:	
DCC-2618: 150 mg QD continuous dosing for 6 week (42 days) cycles.
 
Sunitinib: 50 mg QD in 6 week (42 days) cycles with 4 weeks continuous dosing followed by 2 week break. Dose modifications are allowed per approved package insert or institutional guidelines. Pharmacokinetic (PK)-guided dosing is not allowed. Every effort should be made to continue patients on the starting sunitinib dose regimen throughout the first cycle, unless toxicity mandates dose modification.

Route of Administration:	Oral

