21. All Patients (optional): Additional tumor tissue samples may be collected at the EOT visit and/or for patients undergoing medical procedures including resection of metastases while on study or for patients that have disease progression if the patient consents and these samples will be used for further molecular testing of the cancer while treated with study drug.
  22. Radiologic imaging must be performed within 21 days prior to the first dose of study drug. Radiologic imaging performed as standard of care prior to informed consent may be used as the Screening assessment as long as the imaging was performed within 21 days prior to the first dose of study drug. CT scans of the pelvis, abdomen, and chest will be performed at screening. Subsequently, CT scans of the pelvis and abdomen will be performed at Days 1 of Cycles 2-7, and Day 1 of every odd-numbered cycle thereafter (e.g. Cycles 9, 11, 13 etc.) and EOT visit. A scan at the EOT visit is not required if disease progression was previously confirmed by independent radiologic review or if less than 28 days have passed since the last scan was performed. CT scans of the chest will only be performed subsequently, if the patient had lung metastases at screening or in case of lung symptoms (per the Investigator's discretion). Radiologic imaging may be performed up to 7 days prior to the corresponding study visit or post dose at the study visit. Following Cycle 7 Day 1, any initial indication of a partial or complete response based on investigator assessment must be confirmed  $\geq 4$  weeks following initial response. MRI scans of the abdomen/pelvis and CT scan without contrast of the chest can be used for patients who are allergic to radiographic contrast media or at the Investigator's discretion based on the best interest of the patient after discussion with the Sponsor. Additionally, for patients whose local regulatory authority and/or ethics committee has not approved use of CT scans, MRIs may be used. For each patient, the same assessment technique must be used throughout their participation on study unless there is a safety risk as determined by the Investigator. Ultrasound scanning is not an acceptable substitute for CT scanning.  

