Validation of No Disease Progression: If the independent radiologic reviewer validates that there is no disease progression per modified RECIST, the patient will continue to receive study drug. If the Investigator determines clinical progression based upon clinical deterioration and wishes to end treatment, a scan must be performed prior to treatment discontinuation. The scan must be submitted to for independent radiologic review. The basis for determination of progression due to clinical deterioration must be documented in the patient's source documents and electronic case report form. If the Investigator's assessment determines disease progression per modified RECIST, the Investigator should wait for confirmation from the independent radiologic review before discontinuing the patient from treatment. If the Investigator wishes to end treatment due to local progression, without confirmation of progression by independent radiographic review, or before the independent read results are available, the Investigator must reach out to the Sponsor Medical Monitor to discuss.
- 

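### Overall relative dose intensity uses different denominators in the two arms: sunitinib is charged a full 1400 mg for every cycle started, so fully compliant patients stopping on days 1–27 of a cycle score below 100%

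*SAP*

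**What the plan says.** SAP 9.1 plans the same exposure summaries for both arms: "relative dose intensity will be summarized as continuous variables using descriptive statistics", with categories where suitable. The RDI formulas then differ by arm.

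- **Sunitinib, overall (SAP 9.1.2):** "total cumulative dose received)/(Total number of cycles started*[50*7*4" mg), as a percentage. The per-cycle version is also a fixed 1400 mg: "RDI in a cycle will be calculated as (cumulative dose received in the cycle)/(50*7*4 mg").
- **Ripretinib, overall (SAP 9.1.1):** "total cumulative dose)/(treatment duration [days]×150 mg"), as a percentage, where treatment duration runs from first to last dose inclusive. A fallback applies: "If last dose date is unknown, the earliest of the end of treatment date, data cut-off date" (or end of study) and death date is used. SAP 9.1.2 has no such rule.

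The dosing schedule in the protocol synopsis is "Sunitinib: 50 mg QD in 6 week (42 days) cycles with 4 weeks continuous dosing followed by 2 week break"; ripretinib is dosed on all 42 days. Protocol 9.8.4 (Extent of Exposure) gives no RDI formula, and nothing elsewhere in either document prorates the last sunitinib cycle.

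**The concern.** The 4/2 schedule is a good reason to count 28 dosing days per 42-day cycle for sunitinib. It is no reason to charge dosing days that fall after treatment has ended, and to do so in one arm only. For a compliant patient the error has one direction: it can only lower the sunitinib figure.

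Doses omitted just before a permanent stop widen the gap. They count against sunitinib when they fall on days 1–28 of a started cycle. In the ripretinib arm they lie after the last dose and leave the denominator, which can flatter that arm.

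The protocol makes stops early in a cycle plausible. Under footnote 22 of Protocol Table 1, "CT scans of the pelvis and abdomen will be performed at Days 1 of Cycles 2-7" and then on Day 1 of odd-numbered cycles, and when progression is called locally "the Investigator should wait for confirmation from the independent radiologic review before discontinuing the patient from treatment". A new cycle may already have begun by then. Patients who are mid-cycle at data cutoff are affected in the same way.

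The trial is open-label with an active control, and comparing the safety profiles is a stated secondary objective (SAP 2.1.3). Readers use RDI to judge whether the comparator was properly delivered. A lower sunitinib figure could be taken as poorer delivery when part of it comes from the formula.

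**Working it through.** The plan states no numerical RDI, so there is no figure to reproduce. The check evaluates the two formulas.

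**Inputs.** Sunitinib: 50 mg on days 1–28 of each 42-day cycle, hence 50 × 7 × 4 = 1400 mg per cycle (protocol synopsis; SAP 9.1.2). Ripretinib: 150 mg on all 42 days (protocol synopsis; SAP 9.1.1).

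**Compliant patient, last dose on day d of cycle k.**

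- Sunitinib RDI = [1400(k − 1) + 50 × min(d, 28)] / (1400k)
- Ripretinib RDI = 150n / 150n = 100%, with n = 42(k − 1) + d

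| Last dose | Sunitinib | Ripretinib |
|---|---|---|
| Cycle 1 day 14 | 700/1400 = 50% | 100% |
| Cycle 2 day 14 | 2100/2800 = 75% | 100% |
| Cycle 3 day 14 | 3500/4200 = 83% | 100% |
| Cycle 9 day 14 | 11900/12600 = 94% | 100% |
| Cycle 2 day 28 | 2800/2800 = 100% | 100% |

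Over every k from 1 to 29 and d from 1 to 42, sunitinib RDI is below 100% exactly when d is 1–27.

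**Final interruption.** Cycle 1 complete, doses on cycle 2 days 1–7, then held until permanent stop. Sunitinib: (1400 + 350)/2800 = 62.5%. Ripretinib: 49 doses over 49 days = 100%.

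**Illustration A** (assumed: exponential time on drug, every dose taken; simulated).

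| Median time on drug | Mean sunitinib RDI | Median RDI | Share below 80% |
|---|---|---|---|
| 3 months | 83% | 92% | 29% |
| 4 months | 86% | 94% | 24% |
| 6 months | 89% | 96% | 17% |
| 9 months | 91% | 97% | 12% |

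Between 32% and 35% of patients score 100%.

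**Illustration B** (assumed: exponential progression times with a 6-month median, moved to the next Day 1 scan, dosing then continued x days into the new cycle). Mean sunitinib RDI is 100% for x = 0, 81% for x = 3, 84% for x = 7 and 89% for x = 14.

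**Check of the remedy.** With denominator 50 mg × scheduled on-drug days to the last dose, a compliant patient scores 100% for every k and d. Real omissions before the last dose still count. With 7 scheduled doses missed in cycle 1 and the last dose on cycle 2 day 14, the SAP gives sunitinib 1750/2800 = 62.5% against ripretinib 49/56 = 87.5%; the remedy gives 1750/2100 = 83.3% against 87.5%.

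**Per-cycle RDI.** For a cycle cut off at day 14, sunitinib gives 700/1400 = 50%. Ripretinib gives 14/42 = 33% or 14/14 = 100%, depending on how the number of days in the cycle is read; SAP 9.1.1 does not define it.

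**The case against.** The best reply is that little hangs on this. RDI is descriptive, no between-arm test of it is planned, and the same section reports treatment duration, total dose, person-years and dose reductions. That is right and limits the severity, but none of those measures corrects the RDI figure itself.

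The size is also open to challenge. The 50% and 62.5% examples are stops in cycles 1 and 2, and the shortfall shrinks roughly as 1/k. At the 6-month planning median for sunitinib PFS, the median patient in Illustration A loses about 4 points. Illustration B depends wholly on the assumed days of dosing after the scan. Scans may be done up to 7 days before Day 1, in the sunitinib off period, and the investigator may ask the Medical Monitor about stopping before the independent read. Either could end treatment before a new cycle starts, with no shortfall. All of this stands: the algebra is certain, the size is not.

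A third point is that the remedy extends to sunitinib the last-dose denominator criticised above, so final holds drop out of both arms. That is a real loss of information, but it then falls on both arms alike and can be footnoted.

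Two smaller qualifications also stand. The ripretinib fallback for an unknown last dose date can put a compliant patient below 100%. And the 100% result under the remedy is for unmodified 4/2 dosing, whereas sunitinib dose modifications are permitted.

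**Conclusion.** The concern holds. Followed as written, SAP 9.1.2 scores fully compliant sunitinib patients below 100% whenever the last dose, or data cutoff, falls on days 1–27 of a cycle, while SAP 9.1.1 does nothing comparable to ripretinib. The two overall RDI figures are therefore not comparable.

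The individual shortfall is exact arithmetic. The average shortfall depends on when in the cycle patients stop, which the documents do not say: the assumed scenarios run from no loss to a mean loss of about 19 points (100% down to 81%).

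The effect is confined to the descriptive exposure summary and how it is read between arms. The PFS, ORR and OS tests, the alpha and the sample size are untouched. It should be corrected, but it does not threaten the trial's conclusions on efficacy.

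**What to change.** In SAP 9.1.2, replace the overall sunitinib denominator with the planned dose from first to last dose date: 50 mg × the number of scheduled on-drug days (days 1–28 of each 42-day cycle) in that window. Keep the protocol 4/2 schedule as the reference after any schedule change, as the current formula does. For patients still on treatment, use the last dose on or before data cutoff. Because the new denominator needs a last dose date, carry the unknown-last-dose rule from 9.1.1 into 9.1.2.

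For per-cycle RDI, define the number of days in the cycle in 9.1.1 and prorate a truncated last cycle the same way in both arms. The overall ripretinib formula can stay. Add a table footnote that doses omitted after the last dose taken are not counted in either arm.

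The cost is one formula, one fallback sentence, one per-cycle definition and a footnote in the SAP, plus the programming. No new data are needed and no dosing rule changes.
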